Study Objectives:	
Objective:
 
The study is designed with a run-in phase and the continuation phase (Phase II) is to evaluate the safety and efficacy of SCB01A in patients with recurrent or metastatic squamous cell carcinoma of head and neck.
 
Run-in phase
 
Primary Objective:
 
To determine the optimal dose for 3 cycles of i.v. administration of SCB01A on Days 1 and 8 of each cycle in a 3-week cycle
 
Secondary Objective:
 
To evaluate the safety and toxicity for 3 cycles of i.v. administration of SCB01A on Days 1 and 8 of each cycle in a 3-week cycle
 
Phase II
 
Primary Objective:
 
To assess the disease control rate (DCR) at the end of the 9th week (3 cycles, each cycle consists of 21 days) after treatment with SCB01A, according to the Response Evaluation Criteria in Solid Tumors (RECIST) version 1.1.
 
Secondary Objectives:
 
 • To assess the overall survival (OS) rate at 36 weeks after first treatment with SCB01A in patients with recurrent or metastatic squamous cell head and neck cancer who have previously been treated with platinum therapy. • To assess the progression-free survival (PFS) • To assess the PK profile of SCB01A of patients in the run-in phase. • To assess health outcomes using patient-reported European Organization for Research and Treatment of Cancer Quality of Life Questionnaire-C30 (EORTC QLQ-C30) and EORTC QLQ H&N35 questionnaires. • To assess biomarkers relevant to the efficacy and mechanism of action of SCB01A. • To explore the possible association between biomarkers and clinical outcomes
Study Design:	Multicenter, open-label, phase II study of SCB01A administered to patients with recurrent or metastatic squamous cell carcinoma of head and neck. The study will be conducted in two parts.
	Run-in Phase I (Dose Escalation Phase):

The first part of the study involves dose-escalation, in which successive cohorts of three patients (expanded to six patients in the event of a dose-limiting toxicity) will receive escalating doses of SCB01A until 24 mg/m². Dose escalation assessment will be based on tolerability observed during 3 cycles of treatment. An Optimal Dose will be agreed upon.

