During the run-in phase, three patients will be enrolled and will receive 3 cycles of i.v. administration of SCB01A at a dose of 3.25 mg/m² (Dose 1) on Days 1 and 8 of each cycle in a 3-week cycle (Dose 1). If 1 of the three patients experiences a dose limiting toxicity (DLT) during the first 3 cycles, an additional three patients will be enrolled at the same dose level. If 0/6 or 1/6 i.e. ≤ 1 of subjects experienced DLT at the given dose level, the dose of the subsequent cohort will be increased to the next level, then this process will continue until $>1/6$ of subjects experience DLT at certain dose level or the maximum dose in this protocol, 24 mg/m² (Dose 4) is reached.

Patients enrolled in the run-in phase must either complete 3 cycles of study treatment or experience a DLT to be included in the Full Analysis Set (FAS) for the statistical analyses. During the run-in phase, patients who do not complete the 3 cycles of study treatment, and who do not experience a DLT, will be replaced.

Rules for dose escalation for the run-in phase of the study are listed as following:

1. Dose level will start at 3.25 mg/m² (Dose 1) in the 1st Cohort and can be escalated to 12 mg/m² (Dose 2), 18 mg/m² (Dose 3) and 24 mg/m² (Dose 4). If ≤ 1 subjects have DLT in a cohort of 24 mg/m² (Dose 4), the 24 mg/m² (Dose 4) will be determined as the Optimal Dose.
2. If $=1/3$ subjects in a cohort have DLT(s), enrol three more subjects at the same dose level or if ≤ 1 subjects (i.e., 0/3 or 1/6) experience DLT then subjects can be enrolled into the next higher dose level as per below:
 - a) **Dose Level 3.25 mg/m² (Dose 1):** This dose level has been completed as part of protocol amendment #2 and ≤ 1 patient experienced DLT. Patients will be enrolled in the next dose level based on results from 3.25 mg/m² (Dose 1) Cohort.
 - b) **Dose Level 12 mg/m² (Dose 2):** If 1 patient experiences DLT then 3 additional patients to be enrolled in the same dose level. If the total DLT from 6 patients at the same dose level is ≤ 1 , then the study to move to the next higher dose level. If >1 patients have DLT, then 3 patients to be enrolled at the reduced dose of 10 mg/m² (Dose 1a).

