16. Interim and Final Analysis	31
16.1. Interim Analyses	31
16.2. Final Analysis (End of Study).....	31
17. Software	32
18. Tables	33
19. Listings	35
20. Figures	37
21. References	39

1. Introduction

The following Statistical Analysis Plan (SAP) provides the outline for the statistical analysis of the data from SCB01A-21 study. This SAP is based on the study protocol version 3.0 (dated on 25Jul2016).

The planned analyses identified in this SAP may be included in clinical study reports (CSRs), regulatory submissions, or future manuscripts. Also, post hoc analyses not necessarily identified in this SAP may be performed to further examine study data. Any post hoc, or unplanned, exploratory analyses performed will be clearly identified as such in the final CSR.

Note: This study was designed to have two phases, namely run-in phase I (dose escalation phase) and phase II. This study was terminated early in run-in phase I, with eight (8) subjects screened and five (5) subjects enrolled. There was no recruitment for phase II. In light of the small number of subjects enrolled in this study, the SAP will focus on safety data analysis. Efficacy data will be conducted only if there are enough subjects/events, as appropriate, for the analysis methods.

2. Project Overview

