2.1. Description of Overall Study Design and Plan

This is an open-label, phase II study to evaluate SCB01A in patients with recurrent or metastatic squamous cell head and neck cancer, who have received platinum-based treatment. This study was designed with two phases: one run-in phase I (dose escalation phase) and one continuation phase (phase II).

Run-in Phase I (Dose Escalation Phase)

The run-in phase I was to determine the optimal dose for SCB01A to be used in phase II. In the phase I, dose-escalation was involved, in which successive cohorts of three subjects would receive escalating doses of SCB01A until 24 mg/m². Dose escalation assessment would be based on tolerability observed during 3 cycles of treatment. An Optimal Dose would be agreed upon.

Dose level was initiated at 3.25 mg/m² (Dose 1) in the first cohort, and could be escalated to 12 mg/m² (Dose 2), 18 mg/m² (Dose 3) and 24 mg/m² (Dose 4) by an up and down approach. Briefly, at each dose level, if 1 of the three subjects experienced a dose limiting toxicity (DLT) during the first 3 cycles of SCB01A treatment, an additional three subjects will be enrolled at the same dose level. If 0/6 or 1/6 i.e. ≤1 of subjects experienced DLT at the given dose level, the dose of the subsequent cohort would be increased to the next level, then this process would continue until >1/6 of subjects experienced DLT at certain dose level or the maximum dose in this protocol, 24 mg/m² (Dose 4) was reached. This process could continue at a reduced dose level, if >1/6 of subjects experienced DLT at a higher dose level. The reduced dose levels potentially to be tested were specified in the protocol as 10 mg/m² (Dose 1a), 5 mg/m² (Dose 0a), 15 mg/m² (Dose 2a), and 21 mg/m² (Dose 3a).

When the study was terminated in run-in phase I, subjects were recruited only for cohorts of 3.25 mg/m² (Dose 1) and 12 mg/m² (Dose 2).

Phase II

In the phase II of the study additional subjects would be enrolled to evaluate the Optimal Dose as established by review of the safety committee.

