2.5. Randomization and Assignment of Subjects to Treatment Groups

This is an open label study, and no randomization is applicable.

3. Statistical Considerations

Data will be handled and processed according to the sponsor's representative (Novotech (Australia) Pty Ltd) Standard Operating Procedures (SOPs), which are written based on the principles of Good Clinical Practice (GCP).

All data collected on the eCRFs will be presented in the data listings and will be listed and sorted by subject number and visit, where applicable. All summaries will present the data by SCB01A dose level (cohort) and overall (total enrolled subjects), as applicable. Patient data will be separated via cohort and presented for enrolled subjects.

Unless otherwise stated, the following statistical approaches will be taken:

- Continuous variables: Descriptive statistics will include the number of non-missing values (N), mean, standard deviation (SD), median, minimum, maximum.
- Categorical variables: Descriptive statistics will include frequency counts and percentages per category. Percentages will be rounded to one decimal place, with the denominator being the number of subjects in the relevant population with non-missing data, unless otherwise specified.
- Imputation: No missing data will be imputed generally.
- Pharmacokinetic (PK) data: For PK data the arithmetic mean, standard deviation (SD), median, minimum, maximum, geometric mean and coefficient of variation (CV%) values will be presented.
- Confidence intervals (CIs): CIs will be two-sided and will use 95% confidence levels unless specified otherwise.
- Baseline: Baseline values will be defined as the last non-missing observation for each subject prior to the dosing of study medication (i.e. start of infusion on Cycle 1, Day 1).
- Repeat assessments: Repeat assessments will be included in summary presentations (Tables). Only the original values will be used in summary presentations. All repeat assessments captured in the Electronic Data Capture (EDC) system will be presented in the data listings.

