Continuous variables will be reported to the same precision as the source data. Derived variables will be reported using the same precision to the value(s) from which they were derived. For the reporting of descriptive statistics, the mean (95% CI) and median will be reported to 1 decimal place more than the source data; the minimum, and the maximum values will be presented to the same precision as the source data; and standard deviation will be reported to 2 decimal places more than the source data. Rounding is not allowed in the middle of the calculation. It only takes place at the last step to report the final result. Post-dose time points/visits will be calculated relative to start time of infusion on Day 1. Study day will be defined as assessment day minus dosing day +1.

Analysis will be conducted for run-in phase I only. The dose levels (cohorts) will be referred to in the text, tables and listings as follows,

- 3.25 mg/m² (Dose 1)
- 12 mg/m² (Dose 2)
- Total

4. Analysis Populations

The protocol pre-specified the analysis populations of Full Analysis Set, Per-protocol, Safety and PK. However, this study was terminated early with only five (5) subjects enrolled, thus the analysis populations were modified accordingly as follows.

Furthermore, any additional analysis populations not identified in the SAP will be identified in the final CSR as post hoc analyses. This may include the addition of additional study populations or subgroups of interest.

- **Full Analysis Set (FAS):** The FAS consists of all subjects enrolled in the run-in phase. This population will be used for the listing and summary of efficacy, health outcome, and bioanalytical measurement data.
- **Safety population:** The safety population will consist of all subjects who received at least one dose of SCB01A. All safety, treatment exposure, demographic and baseline characteristic data will be listed and summarized using the Safety Population
- **PK population:** The PK population will consist of all subjects who received at least one dose of SCB01A with sufficient post-dose bio-samples collected for PK profile characterization. PK analysis will be conducted using the PK Population.

5. Subject Disposition

All subjects who provide informed consent and are enrolled will be accounted for in this study. Subject disposition will be summarized using the Safety Population.

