$$S = \left\{ 1 - \frac{(RS - 1)}{range} \right\} \times 100.$$

For the symptom scales/items and the global health status formulae/QoL the linear transformation is

$$S = \{ (RS - 1) / range \} \times 100.$$

The range is the difference between the possible maximum and minimum response a patient can select for each scale.

Handling of Missing Values

The psychometrically validated method according to the EORTC manual will be used to handle cases where some questions belonging to a symptom scale, functional scale or global health status are not answered. If at least half of the items from the scale have been answered, the missing items are imputed and will have values equal to the average of those items which are present for that respondent. Otherwise, the raw score of the scale is set to missing.

Interpretation

The scores S computed according to formulae above have the following interpretation:

- a high score for a **functional scale** represents a high / healthy level of functioning
- a high score for the **global health status/QoL** represents a high QoL
- a high score for a **symptom scale/item** represents a high level of symptomatology / problems

Biostatistical methods

The assessment of EORTC QLQ-C30 conducted at screening is regarded as the baseline assessment, as it is taken prior to dosing. Quality of life data will be summarised descriptively. Global health status/QoL, each functional scale, and each symptom scale/item will be summarized using descriptive statistics for each dose level for all time points assessed, including change from baseline for all post-dose assessments. Plots of mean values and 95% confidence intervals by dose level over time will be provided for each scale or item.

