16.2.5.3	Listing of Body Surface Area (BSA)	Safety	
Concomitant Medications			
16.2.5.4	Listing of Concomitant and Prior Medications	Safety	Y
16.2.5.5	Listing of Cancer-Radiation Therapy	Safety	Y
16.2.5.6	Listing of Cancer-Systemic Therapy	Safety	Y
16.2.5.7	Listing of Cancer-Surgery	Safety	Y
Efficacy			
16.2.6.1	Listing of Target Lesions	FAS	Y
16.2.6.2	Listing of Non-Target Lesions	FAS	Y
16.2.6.3	Listing of Tumor Response Evaluation (Based on RECIST)	FAS	Y
16.2.6.4	Listing of Survival Status	FAS	Y
16.2.6.5	Listing of EORTC QLQ-C30	FAS	Y
16.2.6.6	Listing of EORTC QLQ-H&N35	FAS	Y
16.2.6.7	Listing of Eastern Cooperative Oncology Group Performance Status (ECOG-PS)	FAS	Y
PK			
16.2.6.8	Listing of Individual SCB01A Plasma Concentration Data	PK	Y
16.2.6.9	Listing of Individual SCB01A Plasma Pharmacokinetic Parameters by Treatment Cycle/Day	PK	Y
Biomarker			
16.2.6.10	Listing of Biomarker Data (if available)	FAS	
Adverse Events			
16.2.7.1	Listing of Adverse Events	Safety	Y
16.2.7.2	Listing of Serious Adverse Events	Safety	Y
16.2.7.3	Listing of Dose Limiting Toxicity (DLT)	Safety	
16.2.7.4	Listing of Adverse Events Leading to Study Medication Permanently Discontinued or Interrupted	Safety	
Laboratory			
16.2.8.1	Listing of Haematology	Safety	Y

No.	Title	Analysis Population	Listing to be Generated
16.2.8.2	Listing of Biochemistry	Safety	Y
16.2.8.3	Listing of Coagulation	Safety	Y
16.2.8.4	Listing of Urinalysis	Safety	Y
	Vital Signs		
16.2.9.1	Listing of Vital Signs	Safety	Y
	Physical Examination		
16.2.10.1	Listing of Physical Examination	Safety	Y
	ECG		
16.2.11.1	Listing of ECG Values and Findings	Safety	Y

Due to limitation of available data, only those listings marked as 'Y' will be generated.

20.Figures

No.	Title	Analysis Population	Figures to be Generated
	Efficacy		
14.2.1.1	Kaplan-Meier Curve of Progression-free Survival	FAS	Y
14.2.1.2	Kaplan-Meier Curve of Overall Survival	FAS	Y
	Health Outcome		
14.2.2.1a	Plot of Mean Global Health Status Score/QoL with 95% Confidence Interval Over Time (EORTC QLQ-C30)	FAS	Y
14.2.2.1b	Plot of Mean Physical Functioning Score with 95% Confidence Interval Over Time (EORTC QLQ-C30)	FAS	
14.2.2.1c	Plot of Mean Role Functioning Score with 95% Confidence Interval Over Time (EORTC QLQ-C30)	FAS	
14.2.2.1d	Plot of Mean Emotional Functioning Score with 95% Confidence Interval Over Time (EORTC QLQ-C30)	FAS	

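### The one retained quality-of-life figure (SAP Figure 14.2.2.1a) plots a mean with 95% CI for a 12 mg/m² cohort of at most two patients, where a t-interval has zero width, exceeds the whole 0–100 scale, or does not exist

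*SAP*

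**What the plan says.** **The interval.** SAP 11.1 (EORTC QLQ-C30, Biostatistical methods) states: "Plots of mean values and 95% confidence intervals by dose level over time will be provided for each scale or item". SAP 20 cuts the figures down to those marked Y. Of the 33 quality-of-life plots listed (15 for QLQ-C30, 18 for H&N35), only Figure 14.2.2.1a keeps a Y. It is the plot of the mean global health status/QoL score with its 95% CI over time, on the FAS, which SAP 4 redefines as all subjects enrolled in the run-in.

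**General rules.** SAP 3 says "CIs will be two-sided and will use 95% confidence levels unless specified otherwise" but does not say whether the quantile is t or normal. Its default list for continuous variables is N, mean, SD, median, minimum and maximum, with no CI. Its precision rule adds that "the mean (95% CI) and median will be reported to 1 decimal place more than the source data".

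**Numbers.** SAP 1 reports that the study stopped early "with eight (8) subjects screened and five (5) subjects enrolled". SAP 2.1 adds that "subjects were recruited only for cohorts of 3.25 mg/m² (Dose 1) and 12 mg/m² (Dose 2"). The Protocol Synopsis (Study Design) sets cohorts of three, expanded to six after a DLT, and says of 3.25 mg/m²: "This dose level has been completed as part of protocol amendment #2 and ≤ 1 patient experienced DLT".

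**The concern.** A 95% CI for a mean from one or two patients says almost nothing about the mean. On a bounded, coarsely stepped score it also misleads to the eye. The bar either vanishes, which looks like certainty, or runs outside the range of scores that can occur. Health outcomes are a named secondary endpoint and this is their only retained figure. The SAP sets no minimum n for drawing an interval here. For PFS and OS, by contrast, SAP 10 and 10.2 provide a fallback to simple descriptive statistics when there are no events.

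**Working it through.** The documents give no figure to reproduce, so the check builds the interval from the SAP's own scoring rules.

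**1. Cohort size (inferred).**
- Total enrolled: 5 (SAP 1), all at Dose 1 or Dose 2 (SAP 2.1).
- Dose 1 was completed (Protocol Synopsis), and a cohort is at least 3, so Dose 1 ≥ 3.
- Dose 2 ≤ 5 − 3 = 2. Because Dose 2 was opened and recruited to, it has 1 or 2.
- This is an upper bound. A replacement patient at Dose 1 would make Dose 2 smaller.

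**2. Possible scores.** The scale uses items 29 and 30, each answered 1 to 7 (range 6).
- RS = (Q29 + Q30)/2, which moves in steps of 0.5.
- S = (RS − 1)/6 × 100, which moves in steps of 0.5/6 × 100 = 8.33.
- There are 13 possible values: 0, 8.33, …, 100.
- If one item is missing, the SAP 11.1 rule still gives a value on this grid, so the step does not shrink.

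**3. t-interval at n = 2 (assumed method).** Let d be the difference between the two patients. Then SD/√2 = d/2 and t(0.975, 1) = 12.706.
- Full width = 2 × 12.706 × d/2 = 12.706 × d.
- d = 0 gives width 0.
- d = 8.33 gives half-width 52.9 and width 105.9.
- d = 100 gives width 1270.6.
- Enumerating every pair of possible scores finds none with a width above 0 and up to 100.
- Example: scores of 50 and 58.3 give a mean of 54.2 and a CI of 1.2 to 107.1.

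**4. n = 1.** The SD is undefined, so there is no interval.

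**5. Normal quantile at n = 2.**
- Width = 1.96 × d, so the smallest non-zero width is 1.96 × 8.33 = 16.3.
- Coverage for normally distributed scores is P(|t₁| < 1.96) ≈ 0.70, not 0.95. At n = 3 it is about 0.81.

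**6. The 3.25 mg/m² cohort on the same plot, at n = 3.** t(0.975, 2) = 4.303, so half-width = 4.303 × SD/√3 = 2.484 × SD.
- Assumed SD 15: ±37.3. Assumed SD 20: ±49.7. Assumed SD 25: ±62.1. The documents give no SD.
- The smallest non-zero width is 23.9, so the zero-or-over-100 pattern does not apply.
- If one of three patients misses a visit, that visit falls back to the n = 2 case.

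**The case against.** **The SAP already allows for small numbers.** SAP 1 puts the focus on safety and limits efficacy analysis to cases with enough subjects for the method. SAP 2.3 lists the questionnaires under efficacy, and SAP 11 calls the health-outcome analyses primarily descriptive. All but one of the quality-of-life plots have been dropped. This shows awareness of the problem, but Figure 14.2.2.1a keeps its Y, so the caveat was not applied to it.

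**Individual data will be reported anyway.** A reader might infer that the patients' actual scores would be hidden. The SAP does not support that. Listing 16.2.6.5 (QLQ-C30) is marked Y. Table 14.2.2.1 is also marked Y, and its default minimum and maximum are, at n = 2, the two patients' scores. The defect lies in the figure, not in the report as a whole.

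**SAP 3 does not itself order a CI.** A reader might infer from its precision rule that every cohort mean must carry a 95% CI, or that SAP 3 contradicts itself because its default list has none. Neither follows. A rule on decimals can cover CIs wherever another section calls for one, and SAP 11.1 does. Editing SAP 3 alone would leave the plotted interval in place.

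**The width result is conditional.** It needs n = 2 and a t quantile, and the SAP names no quantile. That objection stands as a limit on the claim. It does not rescue the plot, because the normal alternative would carry a 95% label with about 70% coverage.

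**Conclusion.** The point holds for the 12 mg/m² cohort in Figure 14.2.2.1a. With a t-interval, the error bar at n = 2 is either zero or at least 105.9 points wide on a 100-point scale, and at n = 1 it cannot be drawn. This rests on two assumptions: that Dose 2 has at most two patients, and that the usual t-interval is used.

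It would be tempting to say that the whole figure carries no information, or that the trial's conclusions are at risk. The documents support neither. The 3.25 mg/m² intervals are wide but not degenerate at n = 3, and no test, decision rule or dose decision uses this figure. The same plot instruction in SAP 11.2 has no practical effect, because no H&N35 figure is retained. This is a minor reporting correction.

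**What to change.** In SAP 11.1 and in the title of Figure 14.2.2.1a, replace the mean with 95% CI by dose level with individual patient profiles: global health status/QoL score over time, one line per patient, marked by cohort, on a fixed 0–100 axis, with no interval drawn. Keep the default N, median and minimum–maximum in Table 14.2.2.1. The SAP already takes this approach for PK, where individual concentration profiles are retained (Figure 14.2.3.3b, marked Y).

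The cost is a short wording change and one re-programmed figure. The figure loses its error bar. At 12 mg/m² nothing usable is lost; at 3.25 mg/m² a wide interval is lost, and the individual lines show the spread directly. The exact CIs for DCR in SAP 10.1 are not affected.

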9.1. Adverse Events

Adverse events (AEs) will be coded using the Medical Dictionary for Regulatory Activities (MedDRA®, Version 19.1 or higher), and data will be summarized by System Organ Class (SOC) and Preferred Term (PT). The number and percent of subjects reporting each AE will be summarized for each dose level (cohort) and overall. A subject with two or more AEs within the same level of summarization (i.e., SOC or PT) will be counted only once in that level using the most severe (i.e., highest severity/grade) event or most related (for the relationship to study drug table). Percentages will be based on the number of subjects in the Safety Population within each dose level (cohort). The number of AEs reported will also be presented.

Treatment-emergent AEs (TEAEs) are defined as pre-treatment existing conditions that worsen after study drug administration, or events that occur during the course of the study during or after administration of study drug. Only TEAEs will be included in the AE summary tables which will present data by dose level (cohort). The cohorts to be included in each table are listed in section 3. In the case of a missing AE start date or stop date, the most conservative approach will be followed to classify AE into TEAE.

An overall summary of AEs will be produced including the number of TEAEs; the number and % of subjects reporting at least one: TEAE, serious TEAE, Dose Limiting Toxicity (DLT), grade 3 or higher TEAE, TEAE related to study treatment (possibly, probably, or definitely related), serious TEAE related to study treatment, grade 3 or higher TEAE related to the study drug, TEAEs by maximum severity and TEAEs by maximum relationship.

Additional AE tables will be generated as follows:

- TEAEs by SOC and PT
- Study Medication Related TEAEs by SOC and PT
- TEAEs by (Maximum) Severity
- TEAEs by (Maximum) Relationship to Study Medication
- Grade 3 or Higher TEAE by SOC and PT
- Treatment Emergent SAEs
- Study Medication Related SAEs by SOC and PT
- Dose Limiting Toxicity (DLT) by SOC and PT
- TEAEs Leading to Study Medication Permanently Discontinued
- TEAEs Leading to Study Medication Interrupted
- TEAEs Leading to Death
- Duration from Last Dosing to the Start of TEAE (days of each TEAE since its immediate last dosing)

A by-subject AE data listing, including verbatim term, MedDRA SOC and PT, severity, outcome and relationship to study treatment, will be provided. A separate listing will be generated for SAEs.

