3.1. Description of Overall Study Design and Plan

This study is a single arm, open-label, Phase II trial. There will be two phases in this study, the run-in phase and the continuation phase (Phase II). Phase II will consist of 2 stages.

Run-in Phase

During the run-in phase, three patients will be enrolled and will receive 3 cycles of i.v. administration of SCB01A at a dose of 3.25 mg/m^2 on Days 1 and 8 of each cycle in a 3-week cycle (Dose 1). If one of the three patients experienced a Dose Limiting (DLT) during the first 3 cycles, an additional three patients will be enrolled at the same dose level (Dose 1). If ≤ 1 of subjects experienced DLT at the given dose level, the dose of the subsequent cohort will be increased to the next level, then this process will continue until $\geq 2/3$ or $2/6$ of subjects experience DLT at certain dose level or the maximum dose(Dose 4) in this protocol, 24 mg/ m^2 is reached.

Rules for dose escalation for the run-in phase of the study are listed as following:

1. If 0/3 subjects have a DLT, escalate to the next higher dose level with a cohort of three subjects, unless the maximum dose to be tested in this study, i.e. 24 mg/m^2 (Dose 4). If 0/3 subjects have DLT in a cohort of 24 mg/m^2 (Dose 4), the 24 mg/m^2 (Dose 4) will be determined as the Optimal Dose.
2. If 1/3 subjects have DLT(s), enrol three more subjects at the same dose level:
 - a) If the dose for the cohort is less than 24 mg/m^2 (Dose 4) and 1/6 subjects have DLT(s), escalate to the next higher dose level;
 - b) If the dose for the cohort is higher than 3.5 mg/m^2 (Dose 1) and $> 1/6$ subjects have a DLT, de-escalate to the next dose level (0a, 1a, 2a or 3a) with 3 subjects .
 - c) If > 1 out of 6 subjects in the next lower dose (0a, 1a, 2a or 3a) have DLT(s), then the previous dose will be defined as the MTD.
 - d) If ≤ 1 out of 6 subjects in the next lower dose (0a, 1a, 2a or 3a) have DLT(s), then that dose will be defined as the Optimal Dose.
3. If the dose for the cohort is 24 mg/m^2 (Dose 4) and $1 \leq 6$ subjects have a DLT, then the dose level of 24 mg/m^2 (Dose 4) will be determined as the Optimal Dose.

Patients enrolled in the run-in phase must either complete 3 cycles of study treatment or experience a DLT to be included in the Full Analysis Set (FAS) for statistical analyses. During the run-in phase, patients who do not complete the 3 cycles of study treatment, and do not experience a DLT, will be replaced.

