8.3. Populations for Analysis

Patients will be categorized into the following populations for analysis:

FAS: The FAS consists of all patients enrolled in the run-in phase who either completed at least 3 cycles of study treatment or experience a DLT, and all patients enrolled in the continuation phase (Phase II).

Per-protocol (PP) population: The PP population will consist of all patients who completed at least 3 cycles of study treatment regimen defined for Phase II, have measurable baseline disease and at least one post-baseline RECIST assessment (PD, SD, PR or CR). Patients with a major protocol violation, or AE, deemed by the Medical Monitor to have an impact on the study endpoints will be excluded from the PP population.

Safety population: The safety population will consist of all patients who received at least one dose of SCB01A, and have at least one post-dose safety evaluation.

PK population: The PK population will consist of all patients who received at least one dose of SCB01A with sufficient post-dose bio-samples collected for PK profile characterization.

Details of any other populations for analysis will be described in the SAP.

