16.2. Final Analysis (End of Study)

The final end of study analysis, post the data base lock, will be based on the final version of the SAP.

17. Software

The following software will be used to perform the statistical analyses: SAS® Version 9.2 or higher (SAS Institute, Cary, North Carolina, USA)

18.Tables

No.	Title	Analysis Population	Table to be Generated
	Disposition and Baseline Data		
14.1.1.1	Summary of Disposition and Analysis Populations	Safety	Y
14.1.1.2	Summary of Demographics	Safety	Y
14.1.1.3	Summary of Baseline Never Conduction Velocity by NCI Grade	Safety	
	Efficacy		
14.2.1.1	Summary of Tumor Response and Disease Control Rate	FAS	Y
14.2.1.2	Summary of Progression-free Survival	FAS	Y
14.2.1.3	Summary of Overall Survival	FAS	Y
	Health Outcome		
14.2.2.1	Summary of EORTC QLQ-C30 (Version 3.0) Over Time	FAS	Y
14.2.2.2	Summary of EORTC QLQ-H&N35 Over Time	FAS	Y
14.2.2.3	Summary of Eastern Cooperative Oncology Group Performance Status (ECOG-PS)	FAS	
	PK		
14.2.3.1	Summary of Plasma Concentrations of SCB01A by Dose Level	PK	Y
14.2.3.2	Summary of Plasma Pharmacokinetic Parameters of SCB01A by Dose Level and Treatment Cycle/Day	PK	Y
	Biomarker		
14.2.4.1	Summary of Biomarker Data (if available)	FAS	
	Study Treatment		
14.3.1.1	Summary of Dose Delay, Dose Omission and Early Study Drug Discontinuation	Safety	
14.3.1.2	Summary of Body Surface Area (BSA, m ²)	Safety	
	Adverse Events		
14.3.2.1	Overall Summary of Treatment Emergent Adverse Events	Safety	Y
14.3.2.2	Summary of Treatment Emergent Adverse Events by SOC (System Organ Class) and PT (Preferred Term)	Safety	Y
14.3.2.3	Summary of Related Treatment Emergent Adverse Events by SOC (System Organ Class) and PT (Preferred Term)	Safety	Y
14.3.2.4	Summary of Treatment Emergent Adverse Events by Maximum Severity	Safety	
14.3.2.5	Summary of Treatment Emergent Adverse Events by Maximum Relationship to Study Medication	Safety	
14.3.2.6	Summary of Grade 3 or Higher Treatment Emergent Adverse Events by SOC (System Organ Class) and PT (Preferred Term)	Safety	
14.3.2.7	Summary of Treatment Emergent Serious Adverse Events by SOC (System Organ Class) and PT (Preferred Term)	Safety	Y
14.3.2.8	Summary of Related Treatment Emergent Serious Adverse Events by SOC (System Organ Class) and PT (Preferred Term)	Safety	
14.3.2.9	Summary of Dose Limiting Toxicity (DLT) by SOC (System Organ Class) and PT (Preferred Term)	Safety	Y

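### The SAP reports DLT percentages over every treated patient and keeps no set with the protocol's run-in condition (3 cycles completed or a DLT), so early leavers without a DLT count as having tolerated the dose

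*SAP*

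**What the plan says.** **Protocol.** Section 3.1 says that during the run-in "patients who do not complete the 3 cycles of study treatment, and do not experience a DLT, will be replaced"; the Synopsis says the same. Section 8.3 builds the condition into the analysis set: "The FAS consists of all patients enrolled in the run-in phase who either completed at least 3 cycles of study treatment or experience a DLT". Dose escalation in 3.1 is read from DLT counts among 3 or 6 patients, and the run-in primary objective (2.1) is to find the optimal dose. Section 8.4 asks for the number and percentage of patients with a DLT by dose, in the same sentence as adverse events, and names no denominator.

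**SAP.** Section 4 says that the trial stopped early with five subjects enrolled, and "thus the analysis populations were modified accordingly as follows". The new definitions are "The FAS consists of all subjects enrolled in the run-in phase" and "The safety population will consist of all subjects who received at least one dose of SCB01A". Section 9.1 puts the number and percentage of subjects with a DLT in the overall adverse event summary (Table 14.3.2.1) and sets the denominator: "Percentages will be based on the number of subjects in the Safety Population within each dose level (cohort". In Section 18, Table 14.3.2.9, "Summary of Dose Limiting Toxicity (DLT) by SOC (System Organ Class) and PT (Preferred Term"), is assigned to the Safety population and marked for output.

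**The concern.** A DLT is judged over a window, here the first 3 cycles. A patient who leaves inside that window without a DLT has neither had the event nor shown that the dose was tolerated. The protocol deals with this by replacing such patients and leaving them out of the run-in analysis set. With the SAP's definitions they return to the denominator, and no other SAP set leaves them out.

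What is at stake is how the report reads. The SAP says that it will focus on safety, and DLTs are what the run-in was set up to count. The DLT table would rest on a different basis from the one the protocol uses to count run-in patients for dose decisions. A 0% could also be read as evidence of tolerability when few patients, or none, completed the window.

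**Working it through.** The documents state no DLT rate, and SAP 2.4 gives the run-in no calculated sample size. There is therefore no planned figure to reproduce. The check is which ratios the two definitions can give.

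**Inputs**
- 5 subjects enrolled, none in Phase II (SAP 1).
- Only Dose 1 and Dose 2 recruited (SAP 2.1).
- Dose 1 completed (protocol Synopsis, dose escalation rules).
- One DLT in the first 3 patients requires 3 more at that dose; 0/3 allows escalation (protocol 3.1).

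**Assumptions**
- All 5 enrolled subjects were dosed.
- Dose 1 was completed with at least 3 evaluable patients.
- Dose 2 has at least 1 patient.

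**Step 1: direction.** Let d be patients with a DLT, e the evaluable patients, and k the dosed patients who neither completed 3 cycles nor had a DLT. The protocol basis gives d/e and the SAP gives d/(e + k). None of the k patients had a DLT, so for d > 0 and k > 0 the SAP figure is always the lower one. For d = 0 both are 0%, and only the denominator differs.

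As an illustration of the rule only:
- 1/3 = 33.3% becomes 1/4 = 25.0% with one such patient and 1/5 = 20.0% with two.
- 2/6 = 33.3% becomes 2/7 = 28.6% and 2/8 = 25.0%.

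**Step 2: what is possible here.** With at least 1 of the 5 at Dose 2, Dose 1 has at most 4. With at least 3 at Dose 1, Dose 2 has 1 or 2. A completed Dose 1 with one DLT would need 6 patients, which is more than 5, so Dose 1 had no DLT. The illustrations in Step 1 need a DLT in a cohort of 4 or more, so they cannot occur in this trial.

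**Step 3: possible differences**

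| Column | Protocol condition | SAP Safety basis |
|---|---|---|
| Dose 1 | 0/3 or 0/4 = 0% | 0/3 or 0/4 = 0% |
| Dose 2, one DLT, one non-evaluable | 1/1 = 100% | 1/2 = 50% |
| Total, one DLT at Dose 2, one non-evaluable in either cohort | 1/4 = 25% | 1/5 = 20% |
| Dose 2, no DLT, one of two non-evaluable | 0/1 | 0/2 = 0% |
| Dose 2, no DLT, none evaluable | 0/0, no estimate | 0/1 or 0/2 = 0% |

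Every other split of the 5 subjects gives the same percentages on both bases.

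**The case against.** The case for leaving the SAP alone is a fair one.

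- **No decision depends on the table.** The protocol gives escalation and the choice of dose to the safety committee, which works from counts by cohort. The trial stopped in the run-in, and the SAP's safety analyses are descriptive. This stands. A reader might infer that the diluted rate could have distorted escalation or the optimal dose; nothing in the documents supports that.
- **No protocol rule is broken.** Protocol 8.4 names no DLT denominator, and the protocol defines no population called DLT-evaluable; its FAS plays that part in the run-in. The SAP also discloses that it changed the populations. This stands, so the point is about a weak choice of denominator. The stated reason, five subjects, does not by itself explain why the evaluability condition was dropped.
- **The FAS change is not the cause.** The SAP uses the FAS for efficacy, health outcome and bioanalytical data. The DLT figures follow from using the Safety population. Redefining the FAS matters only because it removed the one set that carried the condition.
- **The evaluable set has its own weakness.** It keeps every patient with a DLT and drops early leavers without one, so membership depends on the outcome. At Dose 2 it could give 100% from one patient. The proportion among all treated patients is a legitimate descriptive figure. This stands, and is the reason to show both.
- **The listings allow a reconstruction.** Disposition, drug administration, early discontinuation and adverse event listings are marked for output, so five patients can be traced by hand. The DLT listing (16.2.7.3) is not marked, however, and the adverse event listing fields named in SAP 9.1 include no DLT flag.

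**Conclusion.** The point holds as a minor reporting weakness. The SAP's DLT percentages count a dosed patient who left early without a DLT as having tolerated the dose, and no SAP set matches the protocol's condition for counting run-in patients.

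Under the assumptions above, Dose 1 cannot change. The largest possible change is from 100% to 50% at Dose 2 and from 25% to 20% in the Total. Both require one DLT at Dose 2 and one non-evaluable patient, and the documents report neither. If there was no DLT, the percentage does not move, but the reader cannot tell from the table how many patients the 0% rests on.

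A reader might conclude that the trial's DLT rate is biased downward. The documents support only that the rule can lower a non-zero rate; they do not show that anyone was replaced or non-evaluable.

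**What to change.** Add a DLT-evaluable set to SAP Section 4 with the protocol's own condition: run-in patients who completed at least 3 cycles or had a DLT. Use it as the denominator for Table 14.3.2.9 and for the DLT row of Table 14.3.2.1. For each cohort and the Total, show the numbers treated, evaluable and non-evaluable, and give the Safety-based n/N alongside. Where no patient is evaluable, print the counts without a percentage. Leave the Safety population as the denominator for all other adverse event summaries.

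The cost is one population flag and one extra column. The drawback is a very small denominator at Dose 2, so counts should be shown with every percentage.
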